3.2.6 Physical Examination

A physical examination was to be performed at Screening.

3.3 Pharmacokinetic Variables

3.3.1 Concentration Data

A plasma sample for analysis of PEX, CIS and TRANS was to be obtained approximately 12 hours after dosing on the previous study day at scheduled visits at Week 1, 2, 4, 6, 8 from Period 1 and at Week 10, 12, 14, 16 from Period 2 and at Week 20, Final visit.

On the morning of Week 1 (after completion of a minimum of 6 days of dosing), patients were to provide a blood sample for the measurement of PEX, CIS and TRANS. These will be used to identify phenotypic Poor Metabolizer (PM), ie a patient whose CIS:PEX ratio is <0.4. Based on these results, PM patients will be immediately withdrawn from study-drug dosing.

On the morning of Week 2 (after completion of a minimum of 13 days of dosing), patients were to provide a blood sample for PEX, CIS and TRANS evaluation. Patients with a CIS:PEX ratio <0.4 will be discussed with the Medical Monitor.

At all assessments from Week 2 onwards, dose adjustment will be considered based on determination of plasma PEX levels.

3.4 Baseline Variables

3.4.1 Prior and Concomitant Medication

Prior medications, received up to and including 30 days prior to the start of study medication, and concomitant medications received at any point during the study were to be recorded in the CRF.

Some medications or drug classes are known to have potential for adverse interactions with PEX. Although, their use was permitted in the protocol, they were to be considered with caution. A list of these agents is included in Appendix A of the protocol.

The original terms recorded on the patient's eCRF for concomitant medications will be standardized by assigning preferred terms from the International Non-Proprietary Name drug terms and procedures dictionary for treatments and surgical and medical procedures.

Medication start and stop dates, recorded on the eCRF, will be used to determine programmatically whether the medications were (i) started and stopped prior to the study period or (ii) used during the study period. To implement this, any medication with a reported stop date that is before the first dose of any study medication will be regarded as a (i) Prior medication. Medications that start before the first dose of any study medication and are continued into the study or start on or after the first dose of any study medication or will be regarded as (ii) Concomitant medication.

3.4.2 Demographic Data

Demographic data, including date of birth, age, sex, race, ethnicity and child bearing potential, were to be recorded at Screening.

3.4.3 Medical History

Medical history, including event or diagnosis description, start and stop dates or ongoing status were to be recorded at Screening. All terms will be coded using the Medical Dictionary for Regulatory Activities (MedDRA).

3.4.4 Coagulation Profile

A coagulation profile was to be performed at Screening only:

- prothrombin time (PT) [Sec]
- partial thromboplastin time (PTT) [Sec]
- international normalized ratio (INR) [None]

3.4.5 CYP2D6 Screening

CYP2D6 was to be assessed at Screening to identify Poor Metabolizer (PM) status, which was to be defined according to the CPIC guidelines.

Any incidences of polymorphisms will be identified and reported under the header CYP2D6 Genotype.

3.5 Study Medication

3.5.1 Compliance and Exposure

Patients were to complete two sequential, 8-week study drug-dosing periods. At the start of Period 1, patients were to commence treatment on 70 mg PEX daily with subsequent dose titration to a plasma level of 100-300 ng/ml (or ug/L) over 8 weeks. During the 8-weeks of Period 2, the dose was to be titrated further to a plasma level of 300-500 ng/ml.

For each of the following study medication accounting periods, the number of tablets dispensed and returned was to be recorded on the CRF and used to derive the number of tablets taken:

Period 1: Day 1 to Week 1
Period 1: Week 1 to Week 2
Period 1: Week 2 to Week 4
Period 1: Week 4 to Week 6
Period 1: Week 6 to Week 8
Period 2: Week 8 to Week 10
Period 2: Week 10 to Week 12
Period 2: Week 12 to Week 14
Period 2: Week 14 to Week 16

For each study medication accounting period an estimate of the total dose and daily dose will be derived from the number of tablets taken. Due to the potential for dose titrations, study medication compliance will not be derived by comparing the number of tablets taken with the intended dose.

Study medication exposure will be derived as the number of days that the patient remained on study medication. Exposure in days will be classified into one of the following categories:

1- 8 days (Week 1)
9- 29 days (Week 4)
30- 43 days (Week 6)
44- 57 days (Week 8)
58- 71 days (Week 10)
72- 85 days (Week 12)
86- 99 days (Week 14)
100-113 days (Week 16)
>113 days

3.5.2 Dose Titration

The dose titration algorithm was to be based on the systemic plasma levels of PEX throughout the dosing regimens in Periods 1 and 2. On the morning of Day 8 (± 1 day) (after completion of a minimum of 6 days of dosing) patients were to provide a blood sample for the measurement of PEX, CIS and TRANS. The analytical results were to be available within 3-5 days of the blood sampling and results for PEX and CIS reported to the study sites and used to determine the following:

- Patients deemed to be phenotypic PMs based on these results were to be immediately withdrawn from study-drug dosing. A phenotypic PM is defined as a patient whose CIS:PEX ratio is <0.4

On the morning of Day 15 (± 1 day) (after completion of a minimum of 13 days of dosing) patients were to provide a blood sample for the measurement of PEX, CIS and TRANS. The analytical results were to be available within 3-5 days of the blood sampling and results for PEX and CIS reported to the study sites and used to determine the following:

- The CIS:PEX ratio will be evaluated and patients with a ratio <0.4 will be further evaluated and the patient status will be discussed with the Medical Monitor.
- Dose adjustment will be decided according to the dose-adjustment algorithm presented in section 4.4.3 and Table 4.1 below.

Subsequent blood samples were to be obtained and plasma levels of PEX, CIS and TRANS determined at the end of Week 4, 6, and 8 in Period 1, and Week 10, 12 and 14 in Period 2.

The following doses were expected to produce therapeutic concentrations in the majority of patients included in the study.

Intermediate Metabolizers (IM)	70 to 140 mg daily
Extensive Metabolizers (EM)	140 to 210 mg daily
Ultra-rapid Metabolizers (UM)	May require maximum doses of: 210 (Period 1) or 280 (Period 2) mg daily.

4 ANALYSIS POPULATIONS

4.1.1 *Safety Population*

The Safety Population will include all patients who receive study drug.

4.1.2 *Modified Intention to Treat Population*

The Modified Intention to Treat Population (MITT) will include all patients who receive study drug and have at least one post-Baseline efficacy assessment.

4.1.3 *Completer Population*

The Completer Population will include all patients who receive study drug and complete all study procedures at Baseline, end of Period 1 and end of Period 2 and have their Period 2 CPEX assessment within 7 days of the target day of 113.

4.1.4 *Pharmacokinetic Population*

The Pharmacokinetic Population will include all patients who receive study drug and had at least one plasma sample collected.

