3.1.2 Secondary efficacy variables

Change from Baseline in VO₂MAX to end of Period 1 compared to Period 2 and Change from Baseline in VO₂MAX to end of Period 1

The change and percent change from Baseline in VO₂MAX to the end of study-drug dosing Period 1 and Period 2 will be derived:

Change at Period 1 = Period 1 VO₂MAX – Baseline VO₂MAX

Percent Change at Period 1 = (Period 1 VO₂MAX – Baseline VO₂MAX)/Baseline VO₂MAX

Change at Period 2 = Period 2 VO₂MAX – Baseline VO₂MAX

Percent Change at Period 2 = (Period 2 VO₂MAX – Baseline VO₂MAX)/Baseline VO₂MAX

As in the primary endpoint, the VO₂MAX at the Day 1 assessment will be regarded as Baseline.

In the same way as for the primary endpoint, if the patient withdraws from the study early, but provides an unscheduled or early end-of-Period 1 or end-of-Period 2 VO₂MAX assessment then this VO₂MAX assessment will be used in the derivation of efficacy endpoints. Only if the unscheduled or early end-of-Period 1 or end-of-Period 2 VO₂MAX assessment is within ±7 days of the intended target assessment (Period 1 target = Day 57; Period 2 target = Day 113), relative to Day 1, will the derived change in VO₂MAX values be used in the principal analysis of this endpoint using the Completer Population (see sections 7.2.1 and 7.2.2).

6 Minute Walk Test

A 6-minute walk test (6MWT) was to be performed at the Baseline (Day 1) assessment and repeated at the end of Period 1 (Week 8) and the end of Period 2 (Week 16).

The change and percent change from Baseline at the end of study-drug dosing Period 2 and the change and percent change from Baseline at the end of study-drug dosing Period 1 will be derived, taking the Day 1 assessment as Baseline.

If a patient withdraws from the study early, but provides an end-of-Period 1 or end-of-Period 2 assessment then this assessment will be used in the derivation of the efficacy endpoints. As in the analysis of the primary endpoint, only if the unscheduled or early end-of-Period 1 or end-of-Period 2 6MWT assessment is within ±7 days of the intended target assessment (Period 1 target = Day 57; Period 2 target = Day 113), relative to Day 1, will the derived change in 6MWT values be used in the principal analysis of this endpoint using the Completer Population (see section 7.2.3 and 7.2.4).

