The Baseline value for each parameter will be identified as the last assessment value taken prior to the start of study medication. For most parameters and most patients, this will be taken as the Screening assessment, however, if any patients have an unscheduled assessment after their Screening assessment and before starting study medication, this will be used. The change and percentage change from Baseline to the end of Period 1 (Week 8), end of Period 2 (Week 16), and Follow-up (Week 20) assessment will also be derived.

Biomarker Hemoglobin A1c Testing

Sampling for biomarker levels of hemoglobin A1c was to be performed at Screening, and repeated at the end of the Period 1 (Week 8), at the end of Period 2 (Week 16), and at the Follow-up (Week 20) assessment.

- Hemoglobin A1c (HbA1c) [%]

The Baseline HbA1c value will be identified as the last assessment value taken prior to the start of study medication. For most patients, this will be taken as the Screening assessment, however, if any patients have an unscheduled assessment after their Screening assessment and before starting study medication, this will be used. The change and percentage change from Baseline to the end of Period 1 (Week 8), end of Period 2 (Week 16) and Follow-up (Week 20) assessment will also be derived.

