5.3 Handling of Dropouts and Missing Data

If the patient withdraws from the study early, but provides an unscheduled or early end-of-Period 1 or end-of-Period 2 VO_{2MAX} assessment then this VO_{2MAX} assessment will be used in the derivation of efficacy endpoints. Only if the unscheduled or early VO_{2MAX} assessment is within ± 7 days of the intended target assessment relative to Day 1, will the derived change in VO_{2MAX} be used in the primary analysis using the Completer Population (see section 7.1, below), but will be used in the supportive analysis, based on the MITT.

Dates will be printed in ISO 8601 date format (YYYY-MM-DD). If only year and month are available, date will be displayed as YYYY-MM. If only year, then just YYYY. Dates that are missing because they are not applicable for the patients are output as “NA”, unless otherwise specified.

Adverse events with missing start dates will be considered as treatment-emergent unless the partial date excludes that possibility, e.g. the adverse event month is prior to the treatment month.

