7.2 Secondary Efficacy Analyses

7.2.1 *Difference between Period 2 and Period 1 Change from Baseline in VO₂MAX*

The first secondary efficacy endpoint is the change from Baseline of VO₂MAX at the end of Period 1 compared to the change from Baseline at the end of Period 2. This will be analyzed using an ANCOVA with covariates of baseline VO₂MAX and the Period-mean plasma PEX level for the Completer Population. The estimated mean change in VO₂MAX from Baseline to Period 1 and to Period 2 and the difference between Period 1 and Period 2 will be presented along with a 95% confidence interval and the p-value. This analysis will be repeated for the MITT, and will include any imputed change in VO₂MAX as in the primary analysis.

Example SAS code is shown below:

```
proc mixed data=dataP1P2;  
  class Period;  
  model CHG=BASE PEXP1P2 Period/ solution cl;  
  lsmeans Period/ cl diffs;  
  estimate "Period 2 vs. Period 1" Period -1 1/ cl;  
run;
```

7.2.2 *Change from Baseline in VO₂MAX at the end of Period 1*

The second secondary efficacy endpoint is the change from Baseline of VO₂MAX at the end of Period 1. Similar to the primary efficacy endpoint, this will be analyzed using an ANCOVA with covariates of baseline VO₂MAX and the Period 1 mean plasma PEX level for the Completer Population. This will be repeated for the MITT, including any imputed change in VO₂MAX values for patients who did not complete the study to the end of Period 1. Descriptive statistics of the Baseline value, VO₂MAX at the end of Period 1 and the change from Baseline to end of Period 1 will be presented for the Completer Population and the MITT Population.

7.2.3 *Change from Baseline in 6MWT at the end of Period 2*

The change from Baseline in the 6MWT at the end of Period 2 will be analyzed using an ANCOVA with covariates of baseline VO₂MAX and the Period 2 mean plasma PEX level. This will be presented for the Completer Population and repeated for the MITT including any imputed change from Baseline values for patients who did not complete the study to the end of Period 2.

7.2.4 *Difference between Period 2 and Period 1 Change from Baseline in 6MWT*

The change from Baseline in the 6MWT at the end of Period 1 compared to the change from Baseline at the end of Period 2 will be analyzed using an ANCOVA with covariates of baseline VO₂MAX and the Period-mean plasma PEX level Completer Population and repeated for the MITT.

7.2.5 *Change from Baseline in 6MWT at the end of Period 1*

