The change from Baseline in the 6MWT at the end of Period 1 will be analyzed using an ANCOVA with covariates of baseline VO_{2MAX} and the Period 1 mean plasma PEX level. This will be presented for the Completer Population and repeated for the MITT including any imputed change from Baseline values for patients who did not complete the study to the end of Period 1.

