8.4 HbA1c

HbA1c data will be listed for each subject in the Safety Population with values outside the normal reference ranges flagged as low or high.

The change from Baseline to the end of Period 2 will be analyzed using an ANCOVA with a covariate of baseline HbA1c for the Completer Population.

The difference between the change from Baseline at the end of Period 1 compared to the change from Baseline at the end of Period 2 will be analyzed using an ANCOVA with a covariate of baseline HbA1c for the Completer Population.

The change from Baseline to the end of Period 1 will be analyzed using an ANCOVA with a covariate of baseline HbA1c for the Completer Population.

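### The principal Period 1 analyses use a Completer set defined by Week 16, so valid Baseline and Week 8 pairs are dropped for later events; this matters mainly for VO2MAX.

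*SAP*

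**What the plan says.** **Population.** SAP 4.1.3 requires Completer patients to have received study drug and to "complete all study procedures at Baseline, end of Period 1 and end of Period 2". Protocol 8.3 sets the same three-visit requirement for primary, secondary and exploratory endpoints. The SAP adds that the Period 2 CPEX must fall within 7 days of Day 113.

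**Where it is used for Period 1.**
- VO2MAX, SAP 7.2.2: an ANCOVA on baseline VO2MAX and "the Period 1 mean plasma PEX level for the Completer Population", repeated on the MITT.
- 6MWT, SAP 7.2.5: "The change from Baseline in the 6MWT at the end of Period 1 will be analyzed using an ANCOVA", presented for the Completer Population and repeated on the MITT.
- HbA1c, SAP 8.4: the change to the end of "Period 1 will be analyzed using an ANCOVA with a covariate of baseline HbA1c for the Completer Population". No MITT repeat is stated.

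**Early-withdrawal rule.** For VO2MAX, SAP 3.1.2 says that an unscheduled or early test from a patient who withdraws must lie within 7 days of its target (Day 57 or Day 113) to "be used in the principal analysis of this endpoint using the Completer Population (see sections 7.2.1 and 7.2.2". For 6MWT it names the same two target days, but refers to the "principal analysis of this endpoint using the Completer Population (see section 7.2.3 and 7.2.4" and does not cite 7.2.5. For HbA1c, SAP 3.2.2 fixes the baseline ("The Baseline HbA1c value will be identified as the last assessment value taken prior to the start of study medication") and gives no early-withdrawal rule. SAP 5.3 says of VO2MAX tests outside the window that they are kept out of the Completer analysis "but will be used in the supportive analysis, based on the MITT".

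**The concern.** A change from Baseline to Week 8 is fully observed at Week 8. Requiring Week 16 procedures as well makes entry to the Period 1 analysis depend on a later event, one that takes place while the patient is being titrated to a higher plasma range. Protocol 2.8 gives the comparison of low and high plasma ranges as a reason for the study, and raises the possibility of equal efficacy with better safety at lower concentrations. The low-range estimate would ideally not be filtered by who gets through the high-range period.

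Two things are at stake. Usable data are lost from the principal analysis. And if leaving in Period 2 is related to the Week 8 response, the Completer mean is shifted.

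The Day 57 rule in 3.1.2 also suggests that its authors expected the Week 8 value of an early withdrawer to be able to reach 7.2.2. Under 4.1.3 it cannot.

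**Working it through.** **1. Following patients through 3.1.2 and 4.1.3.** The windows are 57 ± 7 = Days 50-64 and 113 ± 7 = Days 106-120, so they are at least 106 − 64 = 42 days apart.
- *Withdraws near Day 57, with an early CPEX in Days 50-64.* The test meets the 3.1.2 condition. The patient has no end-of-Period 2 procedures, so 4.1.3 excludes the patient and the Day 57 rule changes nothing.
- *Has the scheduled Week 8 CPEX, then leaves in Period 2 with no Week 16 procedures.* The Period 1 value is neither unscheduled nor early, so 3.1.2 does not address it. 4.1.3 excludes the patient.
- *Completes, but misses a Week 16 procedure or has the Period 2 CPEX outside Days 106-120.* Excluded. Protocol 6.8 allows an invalid end-of-treatment CPEX to be repeated and states no deadline.
- *Leaves late in Period 2, with all end-of-Period 2 procedures done and the CPEX inside Days 106-120.* Stays in.

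**2. Reproducing the plan's power.** Inputs from SAP 11: one-sample t-test, two-sided alpha 0.05, SD 2.5, mean change 1.2 (Period 1) or 2.0 (Period 2), n = 30. Power comes from the noncentral t with n − 1 df and noncentrality mean × √n / SD.
- Period 2: 2.0 × √30 / 2.5 = 4.38, power 98.8% (stated: above 95%).
- Period 1: 1.2 × √30 / 2.5 = 2.63, power 71.9% (stated: 72%). SAP 11 attaches this figure to the first secondary outcome, but it matches the Period 1 change from Baseline, which 7.2.2 calls the second.

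**3. Precision lost.** Protocol 4.1 plans about 33 enrolled and about 30 completing. It does not say when the other 3 leave, so let k of them have a valid Week 8 value. The 95% CI half-width is t(0.975, n − 1) × 2.5 / √n.

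| k | n in a Period 1 set | Power at 1.2 | Half-width (mL/kg/min) |
|---|---|---|---|
| 0 | 30 | 71.9% | 0.934 |
| 1 | 31 | 73.4% | 0.917 |
| 2 | 32 | 74.9% | 0.901 |
| 3 | 33 | 76.2% | 0.886 |

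The Completer analysis stays on the first row. These are t-test figures, as in SAP 11; the planned ANCOVA will differ somewhat.

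**4. Possible bias (assumptions, not document figures).** If 3 of 33 patients are left out and their mean Week 8 change differs from the completers' by a gap g, the Completer mean differs from the all-patient mean by g × 3/33. For g = 1.2 this is 0.11; for g = 2.5 it is 0.23.

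A deliberately extreme model gives a similar range. Suppose that the 3 patients of 33 with the most extreme latent score leave, and that the score has correlation ρ with the Week 8 change. The mean of the top 3 of 33 normal order statistics is 1.721, so the bias is ρ × 2.5 × 1.721 × 3/30 = 0.430ρ in absolute size:
- ρ = 0: 0
- ρ = ±0.25: 0.11
- ρ = ±0.5: 0.22 (0.215/0.934 = 23% of the half-width; 0.215/1.2 = 18% of the assumed effect)
- ρ = ±0.75: 0.32

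In 200,000 simulated trials per case, the nominal 95% interval covered the true mean in about 95%, 94%, 92% and 87% of trials respectively. The sign of the bias follows the sign of ρ, which nothing in the documents fixes.

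**The case against.** **The population is prespecified and has a rationale.** Protocol 8.3 names the Completer Population for secondary and exploratory endpoints, and the SAP follows it. A single set keeps the Period 1 and Period 2 means on the same patients, which suits the ascending-dose objective. This stands, and it is why the comparisons between periods should stay on that set. It is a weaker argument for an analysis of Period 1 alone.

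**Much is already covered.** A Period 2 leaver with a Week 8 test is in the MITT, and 7.2.2 and 7.2.5 are repeated there. The snapshot t-test in SAP 10 uses Period 1 VO2MAX once all patients have completed Week 8. Protocol 8.3 promises a repeat of efficacy on the safety population, and protocol 8.4.6 promises HbA1c summaries at each assessment time. This also stands, in part. The MITT admits out-of-window withdrawal tests, so it need not equal the set of valid Week 8 pairs. The snapshot names no population. SAP 7 does not carry over the safety-population repeat. The Period 1 HbA1c model has no stated second population.

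**Stronger readings that a reader might infer, and that the documents do not support:**
- *That 3.1.2 and 4.1.3 contradict each other.* The window in 3.1.2 is worded as a necessary condition, so nobody has to be both in and out. For VO2MAX it is a rule left without effect for someone who withdraws near Day 57. For 6MWT even that is only implied, because 7.2.5 is not cited. For HbA1c there is no such rule.
- *That the Completer estimate flatters the drug.* No direction can be shown.
- *That three patients is a ceiling.* Both 33 and 30 are approximate, and missed Week 16 procedures or a late CPEX also remove patients. Equally, some of the three may leave before Week 8.
- *That three listed endpoints are affected.* Protocol 8.1.2 lists the Period 1 VO2MAX change on its own. The Period 1 change alone in 6MWT or HbA1c is not listed in 8.1.2 or 8.1.3.

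**Conclusion.** The point holds and is modest. The principal Period 1 analyses are conditioned on events after Week 8. The main case is Period 1 VO2MAX, and there the Day 57 rule does no work for the withdrawals near Week 8 that it describes.

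On the planned loss of about three patients, the cost in precision is at most about 4 percentage points of power and about 0.05 mL/kg/min of half-width, and nothing if all three leave before Week 8. Bias is zero if leaving is unrelated to response. Under the extreme-selection model it is about 0.11 to 0.32 mL/kg/min in either direction, for assumed correlations of 0.25 to 0.75. These figures rest on SAP 11's SD and effect, on a t-test in place of the ANCOVA, and on assumed correlations. The documents give no rate for exclusions by missed Week 16 procedures or an out-of-window CPEX, so the true number dropped could be larger or smaller than three.

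The primary analysis is not affected. This is a cheap improvement worth making; it does not threaten the trial's main conclusion.

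**What to change.** Add to SAP section 4: *Period 1 Evaluable Population: every patient who took study drug and has both a valid Baseline value and a valid end-of-Period 1 value of the endpoint being analyzed. An unscheduled or early VO2MAX or 6MWT test counts only if it lies within 7 days of Day 57.*

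- Make it the principal set for 7.2.2, 7.2.5 and the Period 1 HbA1c analysis in 8.4.
- Keep the Completer result for those analyses as a sensitivity analysis, and keep the MITT repeats.
- In 3.1.2 and 5.3, tie the Day 57 rule to the new set, citing 7.2.2 and 7.2.5, and tie the Day 113 rule to the Completer Population.
- Add the set to the population listing in 6.1, and record the departure from protocol 8.3 in SAP 12.
- Leave 7.1, 7.2.1, 7.2.3, 7.2.4 and the other two HbA1c analyses on the Completer Population.

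SAP 1 allows revisions before database lock. Because the study is open-label and the snapshot reports Period 1 VO2MAX, the change is best dated before the snapshot if that is still possible; otherwise the CSR should state the order of events.

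The cost is one definition, edits to seven sections (3.1.2, 5.3, 6.1, 7.2.2, 7.2.5, 8.4 and 12) and a sensitivity table, with no new data. The downside is that the Period 1 and Period 2 tables may have slightly different N, so their separate means need not come from identical patients. The Period 2 versus Period 1 comparison still uses the same patients.

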8 STATISTICAL CONSIDERATIONS

8.1 PRIMARY AND SECONDARY ENDPOINTS

8.1.1 Primary Endpoint

The primary endpoint of the study is the change from baseline of VO₂MAX at the end of Period 2 of the study.

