8.3 PATIENT POPULATION FOR ANALYSIS

The population for analysis for the primary, secondary and exploratory endpoints will be the Completer Population which will include all patients who complete all study procedures at Baseline, end of Period 1 and end of Period 2.

The population for safety analysis will be the Safety Population which will include all patients who start study-drug dosing following their baseline visit to the study site. The efficacy analysis will be repeated on the safety population

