3 ANALYSIS VARIABLES

3.1 Efficacy Variables

3.1.1 Primary efficacy variable

The primary endpoint of the study is the change from Baseline of VO₂MAX at the end of Period 2. Cardio-Pulmonary Exercise Testing (CPEX) was to be performed at Screening and repeated at Baseline (Day 1), at the end of Period 1 (Week 8) and the end of Period 2 (Week 16). Details of the exercise test performed and the resultant VO₂MAX evaluations were to be reported in the CRF. For entry into the study, the patient's VO₂MAX at Screening could not exceed 75% of the predicted age-adjusted value and the VO₂MAX at Baseline (Day 1) could not be outside $\pm 20\%$ of the Screening VO₂MAX value (if the centralized CPEX assessor deems the Baseline CPEX test is not within $\pm 20\%$ of the Screening CPEX after dosing with study medication has already commenced, the subject will remain in the study and the subject's Baseline CPEX result will be taken as the valid Baseline result, unless it is deemed invalid or if the CPEX test was administered after the start of study medication).

CPEX reports were to be validated by a centralized CPEX assessor.

The VO₂MAX at the Day 1 assessment will be regarded as Baseline unless the CPEX was reported to have been assessed after the start of study medication. If this situation arises, the VO₂MAX from Screening will be regarded as Baseline. Changes and percent changes from Baseline to the end of Period 2 VO₂MAX value will be derived:

$$\text{Change at Period 2} = \text{Period 2 VO}_{2\text{MAX}} - \text{Baseline VO}_{2\text{MAX}}$$

$$\text{Percent Change at Period 2} = (\text{Period 2 VO}_{2\text{MAX}} - \text{Baseline VO}_{2\text{MAX}}) / \text{Baseline VO}_{2\text{MAX}}$$

If the patient withdraws from the study early, but provides an unscheduled or early end-of-Period 2 VO₂MAX assessment then this VO₂MAX assessment will be used in the derivation of efficacy endpoints. Only if the unscheduled or early end-of-Period 2 VO₂MAX assessment is within ± 7 days of the intended target assessment (Period 2 target = Day 113), relative to Day 1, will the derived change in VO₂MAX be used in the primary analysis using the Completer Population (see section 7.1, below).

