7 ANALYSIS OF EFFICACY

7.1 Primary Efficacy Analysis

The primary endpoint is the change from Baseline of VO_{2MAX} at the end of Period 2. This will be analyzed using an Analysis of Covariance (ANCOVA) with covariates of baseline VO_{2MAX} and the mean plasma PEX level, with the mean taken from all available Period 2 assessments (> Week 8 to Week 16). The primary analysis population will be the Completer Population and will include an efficacy endpoint from all patients with an assessment within ± 7 days of the planned assessment. The estimated mean change in VO_{2MAX} from Baseline to Period 2 will be presented along with a 95% confidence interval of the change and the p-value. This analysis will be repeated for the percent change from Baseline of VO_{2MAX} at the end of Period 2, including the same covariates.

Descriptive statistics of the Baseline value, VO_{2MAX} at the end of Period 2 and the change and percent change from Baseline to end of Period 2 will be presented for the Completer Population.

The primary analysis and descriptive statistics table will be repeated for the MITT, and will include any imputed change in VO_{2MAX} values for patients who did not complete the study to the end of Period 2 but provided an end of Period 2 VO_{2MAX} assessment (see section 3.1.1).

Example SAS code is shown below:

```
proc mixed data=dataP2;
  class Period;
  model CHG=BASE PEXALL Period/ solution cl;
  lsmeans Period/ cl;
run;
```

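### The Completer Population makes the primary VO2MAX analysis depend on every scheduled procedure at three visits, and SAP 7.1 describes the same set differently

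*SAP*

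**What the plan says.** Protocol 8.1.1 defines the endpoint: "The primary endpoint of the study is the change from baseline of VO₂MAX at the end of Period 2 of the study". It therefore uses two measurements per patient.

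Protocol 8.3 names the Completer Population for the primary, secondary and exploratory endpoints and defines it as "all patients who complete all study procedures at Baseline, end of Period 1 and end of Period 2". SAP 4.1.3 keeps that condition (patients must "complete all study procedures at Baseline, end of Period 1 and end of Period 2"), requires receipt of study drug, and adds that the Period 2 CPEX must fall within 7 days of Day 113. Neither document limits the procedures to CPEX or to efficacy tests.

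SAP 7.1 states: "The primary analysis population will be the Completer Population". The same sentence continues that it "will include an efficacy endpoint from all patients with an assessment within ± 7 days of the planned assessment". SAP 3.1.1 and 5.3 apply the same window to early-withdrawal tests: such a test enters the Completer analysis only if it lies within 7 days of target.

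SAP 7.1 repeats the primary analysis in the MITT population (treated, with at least one post-Baseline efficacy assessment). SAP 12 calls this a sensitivity population.

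**The concern.** A patient can have everything the primary endpoint requires and still fail SAP 4.1.3. A missed 6MWT at Baseline, Week 8 or Week 16, a missed HbA1c or chemistry sample at Week 8 or Week 16, or a missed Week 8 CPEX would be enough. None of these enters the Week 16 change in VO2MAX.

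Two things are at stake. First, valid primary data may be set aside for reasons unrelated to VO2MAX. If those reasons are associated with how the patient is doing, the remaining patients are a selected group, and a single-arm design has no comparator to absorb that. Second, two programmers following SAP 4.1.3 and SAP 7.1 in good faith could build different primary sets. The trial is open-label, and Period 1 VO2MAX is analysed at the snapshot (SAP 10) before the final analysis, so membership should not be left to later judgement.

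**Working it through.** **1. The two rules side by side.** Take a treated patient with a valid Baseline CPEX, a valid Week 16 CPEX on Day 113 and no 6MWT at Week 8.

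- SAP 4.1.3 and Protocol 8.3: excluded, because one end-of-Period-1 procedure was not completed.
- SAP 7.1, second half of the sentence: included, because the assessment is within the window.
- SAP 3.1.1 and 5.3: do not settle it. Their wording sets a necessary condition for an early test and says nothing about other procedures.

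**2. What the literal rule covers.** Counting measured items in Protocol Table 6.2, without the conditional pregnancy test:

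- Baseline, 5: ECG, CPEX, weight, vital signs, 6MWT.
- Week 8, 8: those five plus chemistry, drug levels and HbA1c.
- Week 16, 9: those eight plus blood count.

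The total is 5 + 8 + 9 = 22. The endpoint uses 2 of them (Baseline and Week 16 CPEX), which leaves 20 others. Chemistry and HbA1c are not Baseline-visit items, and of the three visits the blood count is scheduled only at Week 16.

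The list itself is not fixed. SAP 3.2.4 omits weight at Baseline, where Table 6.2 schedules it. It also counts temperature as a vital sign at all assessments, while footnote I of Table 6.2 names only heart rate and blood pressure.

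**3. The plan's power figures.** Inputs from Protocol 8.2 and SAP 11: mean change 2.0 (Period 2) and 1.2 (Period 1), SD 2.5, two-sided alpha 0.05, n = 30, one-sample t-test. Power comes from the noncentral t distribution with n − 1 degrees of freedom and noncentrality (mean/SD) × √n.

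- Period 2: 0.80 × √30 = 4.38, power 98.8%. The plan states above 95%: reproduced.
- Period 1: 0.48 × √30 = 2.63, power 72%. The plan states 72%: reproduced.

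**4. How much loss the primary power statement tolerates.** The half-width is that of the 95% confidence interval, t(0.975, n − 1) × 2.5/√n.

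| n analysed | power for 2.0 | half-width (mL/kg/min) |
|---|---|---|
| 30 | 98.8% | 0.93 |
| 24 | 96.3% | 1.06 |
| 23 | 95.6% | 1.08 |
| 22 | 94.7% | 1.11 |
| 20 | 92.4% | 1.17 |

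The statement holds for a loss of up to 7 of 30.

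**5. How many might be lost.** The documents give no miss rate, so this is only a range under assumption. If each of k items is missed independently with probability p, the expected number qualifying is 30 × (1 − p)^k.

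| p | k = 12 | k = 20 |
|---|---|---|
| 1% | 26.6 | 24.5 |
| 2% | 23.5 | 20.0 |
| 5% | 16.2 | 10.8 |

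Here k = 20 is the full count from step 2, and k = 12 is a smaller illustrative count. Independence is pessimistic. Several items are blood samples from one visit, misses tend to cluster by visit, and at a fixed miss rate clustering reduces the number of patients lost.

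**6. Selection.** If a share f of patients is dropped and their mean change is lower by D than that of those kept, the retained mean exceeds the full mean by f × D. With f = 20% and D = 1.0 mL/kg/min, both assumed, that is 0.2 × 1.0 = 0.2 mL/kg/min. A negative D reverses the sign.

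**The case against.** The strongest reply is that SAP 7.1 governs the primary analysis and already admits everyone with an in-window assessment, so no one need be dropped. That shows a plausible intent to define the set by CPEX. But the same sentence names the Completer Population, and the definition of that population is unchanged. The conflict stands as a matter of wording to be settled.

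A second reply is that nothing is discarded, because the MITT repeat keeps these patients and Protocol 8.3 repeats the efficacy analysis on the Safety Population. Any divergence would indeed be visible. The MITT result, however, is supportive, and under SAP 5.3 it also admits withdrawal tests from outside the window. It therefore changes two things at once and does not isolate the patients at issue.

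A third reply is that requiring the Week 8 CPEX gives one common set for the primary analysis and the comparison of periods. That is a reasonable aim, but it does not justify requiring the 6MWT or laboratory samples as well.

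Three stronger readings are tempting and not supported:

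- **That SAP 3.1.1 contradicts SAP 4.1.3.** It does not: being within 7 days is stated as a necessary condition, which is compatible with further requirements.
- **That an early withdrawal who completes the whole Protocol 6.11 list must still fail because weight is not on it.** This is doubtful: vital signs are on that list, and SAP 3.2.4 counts weight among them.
- **That fatigued patients will miss the 6MWT because it comes last, inflating the result.** This is conceivable, but no document says so. Footnote D of Table 6.2 explains the test order as a way to help patients complete both exercise tests in one day.

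**Conclusion.** The concern holds as a defect of definition. SAP 4.1.3 and Protocol 8.3, applied as written, exclude patients with complete and valid primary-endpoint data, and SAP 7.1 describes the same set in terms that would include them. The consequence is possible loss of valid data and possible selection in an uncontrolled trial. The size and direction of any effect are unknown; the figures in steps 5 and 6 rest on assumed miss rates and assumed differences.

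A reader might infer that the trial becomes underpowered. The documents do not support that: eight or more of the 30 expected completers would have to be lost before primary power fell below the stated 95%, and nothing in the documents says how many procedures will be missed. This should be fixed before database lock, but it does not invalidate the design.

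**What to change.** Define the primary analysis set as treated patients with:

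- a valid Baseline VO2MAX under the baseline rule of SAP 3.1.1;
- a valid Week 16 VO2MAX within 7 days of Day 113; and
- at least one Period 2 perhexiline level, for as long as the Period 2 mean level stays in the primary ANCOVA. Without one, a patient would be in the set but drop out of the model.

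Require the Week 8 CPEX only for the Period 1 and Period 2-versus-Period 1 VO2MAX analyses. Require the 6MWT only for the 6MWT analyses, together with the covariates those models use. Remove the all-procedures condition, bring SAP 4.1.3, SAP 7.1 and Protocol 8.3 into line, and record the change in SAP 12.

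SAP 1 allows revision before database lock. The cost is a few lines of text and a revised population flag in the programming specification. No new data are needed.
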